12. ADMINISTRATIVE AND LEGAL OBLIGATIONS

12.1 **Protocol Amendments and Study Termination**

If Amgen amends the protocol, agreement from the investigator must be obtained. The IRB/IEC must be informed of all amendments and give approval. The investigator must send a copy of the approval letter from the IRB/IEC to Amgen.

Amgen reserves the right to terminate the study at any time. Both Amgen and the investigator reserve the right to terminate the investigator's participation in the study according to the study contract. The investigator is to notify the IRB/IEC in writing of the study's completion or early termination and send a copy of the notification to Amgen.

Subjects may be eligible for continued treatment with Amgen IP by an extension protocol or as provided for by the local country's regulatory mechanism. However, Amgen reserves the unilateral right, at its sole discretion, to determine whether to supply Amgen IP and by what mechanism, after termination of the study and before the product(s) is/are available commercially.

12.2 **Study Documentation and Archive**

The investigator is to maintain a list of appropriately qualified persons to whom he/she has delegated study duties. All persons authorized to make entries and/or corrections on CRFs will be included on the Amgen Delegation of Authority Form.

Source documents are original documents, data, and records from which the subject's CRF data are obtained. These include but are not limited to hospital records, clinical and office charts, laboratory and pharmacy records, diaries, microfiches, radiographs, and correspondence.

Protocol Number: 20130286 Page 61 of 73

Product: Evolocumab Date: 30 January 2017

In this study, the IVRS/IWRS system captures the following data points and these are considered source data:

The investigator and study staff are responsible for maintaining a comprehensive and centralized filing system of all study-related (essential) documentation, suitable for inspection at any time by representatives from Amgen and/or applicable regulatory authorities.

Elements to include:

- Subject files containing completed CRFs, ICFs, and subject identification list
- Study files containing the protocol with all amendments, Investigator's Brochure, copies of prestudy documentation, and all correspondence to and from the IRB/IEC and Amgen
- Investigational product-related correspondence including Proof of Receipts, IP Accountability Record(s), Return of IP for Destruction Form(s), Final IP Reconciliation Statement, as applicable.

In addition, all original source documents supporting entries in the CRFs must be maintained and be readily available.

Retention of study documents will be governed by the Clinical Trial Agreement.

12.3 **Study Monitoring and Data Collection**

The Amgen representative(s) and regulatory authority inspectors are responsible for contacting and visiting the investigator for the purpose of inspecting the facilities and, upon request, inspecting the various records of the clinical study (eg, CRFs and other pertinent data) provided that subject confidentiality is respected.

The Amgen Clinical Monitor is responsible for verifying the CRFs at regular intervals throughout the study to verify adherence to the protocol; completeness, accuracy, and consistency of the data; and adherence to local regulations on the conduct of clinical research. The Clinical Monitor is to have access to subject medical records and other study-related records needed to verify the entries on the CRFs.

The investigator agrees to cooperate with the Clinical Monitor to ensure that any problems detected in the course of these monitoring visits, including delays in completing CRFs, are resolved.

In accordance with ICH GCP and the sponsor's audit plans, this study may be selected for audit by representatives from Amgen's Global Compliance Auditing function (or designees). Inspection of site facilities (eg, pharmacy, protocol-required therapy storage

Product: Evolocumab Protocol Number: 20130286 Date: 30 January 2017

areas, laboratories) and review of study-related records will occur to evaluate the study conduct and compliance with the protocol, ICH GCP, and applicable regulatory requirements.

Data capture for this study is planned to be electronic:

- All source documentation supporting entries into the CRFs must be maintained and readily available.
- Updates to CRFs will be automatically documented through the software's "audit trail".
- To ensure the quality of clinical data across all subjects and sites, a clinical data management review is performed on subject data received at Amgen. During this review, subject data are checked for consistency, omissions, and any apparent discrepancies. In addition, the data are reviewed for adherence to the protocol and GCP. To resolve any questions arising from the clinical data management review process, data queries are created in the EDC system database for site resolution and subsequently closed by the EDC system or by an Amgen reviewer.
- The investigator signs only the Investigator Verification Form for this electronic data capture study or the investigator applies an electronic signature in the EDC system if the study is set up to accept an electronic signature. This signature indicates that investigator inspected or reviewed the data on the CRF, the data queries, and agrees with the content.

Amgen (or designee) will perform self-evident corrections to obvious data errors in the clinical trial database, as documented in the Study Specific Self Evident Corrections Plan. Examples of obvious data errors that may be corrected by Amgen (or designee) include deletion of obvious duplicate data (eg, same results sent twice with the same date with different visit-week 4 and early termination) and clarifying "other, specify" if data are provided (eg, race, physical examination). Each investigative site will be provided a list of the types of corrections applied to study data at the initiation of the trial and at study closeout.

12.4 Investigator Responsibilities for Data Collection

The investigator is responsible for complying with the requirements for all assessments and data collection (including subjects not receiving protocol-required therapies) as stipulated in the protocol for each subject in the study. For subjects who withdraw prior to completion of all protocol-required visits and are unable or unwilling to continue the Schedule of Assessments (Table 3), the investigator can search publically available records [where permitted] to ascertain survival status. This ensures that the data set(s) produced as an outcome of the study is/are as comprehensive as possible.

Page 62 of 73

Protocol Number: 20130286 Page 63 of 73

Product: Evolocumab Date: 30 January 2017

12.5 Language

All written information and other material to be used by subjects and investigative staff must use vocabulary and language that are clearly understood.

12.6 **Publication Policy**

Authorship of any publications resulting from this study will be determined on the basis of the Uniform Requirement for Manuscripts Submitted to Biomedical Journals (International Committee of Medical Journal Editors), which states:

- Authorship credit should be based on (1) substantial contributions to conception and design, acquisition of data, or analysis and interpretation of data; (2) drafting the article or revising it critically for important intellectual content; (3) final approval of the version to be published. Authors should meet conditions 1, 2, and 3.
- When a large, multicenter group has conducted the work, the group should identify the individuals who accept direct responsibility for the manuscript. These individuals should fully meet the criteria for authorship defined above.
- Acquisition of funding, collection of data, or general supervision of the research group, alone, does not justify authorship.
- All persons designated as authors should qualify for authorship, and all those who qualify should be listed.
- Each author should have participated sufficiently in the work to take public responsibility for appropriate portions of the content.

All publications (eg, manuscripts, abstracts, oral/slide presentations, book chapters) based on this study must be submitted to Amgen for review. The Clinical Trial Agreement among the institution, investigator, and Amgen will detail the procedures for, and timing of, Amgen's review of publications.

12.7 Compensation

Any arrangements for compensation to subjects for injury or illness that arises in the study are described in the Compensation for Injury section of the ICF that is available as a separate document.

Page 64 of 73

Product: Evolocumab Protocol Number: 20130286 Date: 30 January 2017

14. APPENDICES

Product: Evolocumab
Protocol Number: 20130286

Date: 30 January 2017 Page 67 of 73

Appendix A. Additional Safety Assessment Information

Adverse Event Grading Scale

Refer to the NCI Common Terminology Criteria for Adverse Events (CTCAE) Version 4.0. The CTCAE is available at the following link:

http://ctep.cancer.gov/protocolDevelopment/electronic applications/ctc.htm

Drug-induced Liver Injury Reporting & Additional Assessments Reporting

To facilitate appropriate monitoring for signals of DILI, cases of concurrent AST or ALT and TBL according to the criteria specified in Section 6.3 require the following:

- The event is to be reported to Amgen as a serious adverse event within 24 hours of discovery or notification of the event (ie, before additional etiologic investigations have been concluded)
- The appropriate CRF (eg, Event CRF) that captures information necessary to facilitate the evaluation of treatment-emergent liver abnormalities is to be completed and sent to the Amgen.

Other events of hepatotoxicity and potential DILI are to be reported as serious adverse events if they meet the criteria for a serious adverse event defined in Section 9.2.2.2.

Additional Clinical Assessments and Observation

All subjects in whom IP or protocol-required therapies is/are withheld (either permanently or conditionally) due to potential DILI as specified in Sections 6.3.1 and 6.3.2 or are to undergo a period of "close observation" until abnormalities return to normal or to the subject's baseline levels. Assessments that are to be performed during this period include:

- AST, ALT, ALP, and bilirubin (total and direct) is to be repeated within 24 hours
- In cases of TBL > 2x ULN, retesting of liver tests, and bilirubin (total and direct) is to be performed every 24 hours until laboratory abnormalities improve

Product: Evolocumab
Protocol Number: 20130286

Date: 30 January 2017 Page 68 of 73

Testing frequency of the above laboratory tests may decrease if the abnormalities stabilize or the IP or protocol-required therapies has/have been discontinued AND the subject is asymptomatic.

- Initiate investigation of alternative causes for elevated AST or ALT and/or elevated TBL:
 - Obtain complete blood count with differential to assess for eosinophilia
 - Obtain serum total immunoglobulin IgG, Anti-nuclear antibody (ANA), Anti Smooth Muscle Antibody, and Liver Kidney Microsomal antibody 1 (LKM1) to assess for autoimmune hepatitis
 - Obtain serum acetaminophen (paracetamol) levels
 - Obtain a more detailed history of:
 - Prior and/or concurrent diseases or illness
 - Exposure to environmental and/or industrial chemical agents
 - Symptoms (if applicable) including right upper quadrant pain, hypersensitivity-type reactions, fatigue, nausea, vomiting, and fever
 - Prior and/or concurrent use of alcohol, recreational drugs and special diets
 - Concomitant use of medications (including non-prescription medicines and herbal and dietary supplements), plants, and mushrooms
 - Obtain viral serologies
 - Obtain CPK, haptoglobin, lactate dehydrogenase, and peripheral blood smear
 - Perform appropriate liver imaging if clinically indicated
- Obtain appropriate blood sampling for pharmacokinetic analysis if this has not already been collected
- Obtain hepatology consult (liver biopsy may be considered in consultation with an hepatologist)
- Follow the subject and the laboratory tests (ALT, AST, and TBL) until all laboratory abnormalities return to baseline or normal. The "close observation period" is to continue for a minimum of 4 weeks after discontinuation of all IP and protocol-required therapies.

The potential DILI event and additional information such as medical history, concomitant medications and laboratory results must be captured in corresponding CRFs.

Product: Evolocumab Protocol Number: 20130286 Date: 30 January 2017

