4.1.2 Exclusion Criteria

- Subject taking a combination of background lipid-lowering therapy and HIV therapy known to have significant drug-drug interaction as per Table 2
- New York Heart Association III or IV heart failure, or last known left ventricular ejection fraction < 30%
- Known opportunistic infection/AIDS defining illness (including but not limited to candidiasis of bronchi, trachea, esophagus, or lungs, invasive cervical cancer, coccidioidomycosis, cryptococcosis, chronic intestinal (> 1-month duration) cryptosporidiosis, cytomegalovirus disease (particularly cytomegalovirus [CMV] retinitis), HIV-related encephalopathy, herpes simplex: chronic ulcer(s) (> 28 days duration); or bronchitis, pneumonitis, or esophagitis, histoplasmosis, chronic intestinal (> 28 days duration) isosporiasis, Kaposi's sarcoma, lymphoma, mycobacterium avium complex, tuberculosis, pneumocystis carinii pneumonia, recurrent pneumonia, progressive multifocal leukoencephalopathy, salmonella septicemia, toxoplasmosis of brain, or wasting syndrome due to HIV within 1 year prior to randomization
- 204 Myocardial infarction, unstable angina, percutaneous coronary intervention, coronary artery bypass graft or stroke within 3 months prior to randomization
- Type 1 diabetes, new-onset (hemoglobin A1c [HbA1c] ≥ 6.5% or fasting plasma glucose ≥ 126 mg/dL at screening without known diagnosis) or poorly controlled (HbA1c ≥ 10%) type 2 diabetes by central laboratory during screening
- 206 Uncontrolled hypertension defined as sitting systolic blood pressure > 180 mmHg or diastolic blood pressure > 110 mmHg during screening
- Subject has taken a cholesterylester transfer protein inhibitor in the last 12 months prior to randomization
- 208 Moderate to severe renal dysfunction, defined as an estimated glomerular filtration rate < 30 mL/min/1.73 m² during screening

Date: 30 January 2017 Page 21 of 73

209 Persistent active liver disease or hepatic dysfunction defined as Child-Pugh score of C. Stable (in the opinion of the primary investigator and with aspartate aminotransferase [AST] and alanine aminotransferase [ALT] < 5 times ULN and not expected to require new treatment[s] during study) chronic hepatitis C of at least 1 year duration prior to randomization is allowed

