6.3 Hepatotoxicity Stopping and Rechallenge Rules

Permanent Discontinuation

Subjects with abnormal hepatic laboratory values (ie, alkaline phosphatase [ALP], AST, ALT, total bilirubin [TBL]) **and/or international normalized ratio (INR)** and/or signs/symptoms of hepatitis (as described below) may meet the criteria for withholding or permanent discontinuation of Amgen IP or other protocol-required therapies as specified in the Guidance for Industry Drug-Induced Liver Injury (DILI): Premarketing Clinical Evaluation (July 2009).

6.3.1 Criteria for Withholding and/or Permanent Discontinuation of Amgen Investigational Product and Other Protocol-required Therapies Due to Potential Hepatotoxicity

The following stopping and/or withholding rules (Table 1) apply to subjects for whom another cause of their changes in liver biomarkers (TBL, INR and transaminases) has not been identified.

Important alternative causes for elevated AST/ALT and/or TBL values include, but are not limited to:

Hepatobiliary tract disease

Product: Evolocumab

- Viral hepatitis (eg, Hepatitis A/B/C/D/E, Epstein-Barr virus, cytomegalovirus, herpes simplex virus, varicella, toxoplasmosis, and Parvovirus)
- Right-sided heart failure, hypotension or any cause of hypoxia to the liver causing ischemia
- Exposure to hepatotoxic agents/drugs or hepatotoxins, including herbal and dietary supplements, plants, and mushrooms
- Heritable disorders causing impaired glucuronidation (eg, Gilbert's syndrome, Crigler-Najjar syndrome) and drugs that inhibit bilirubin glucuronidation (eg, indinavir, atazanavir)
- Alpha-one antitrypsin deficiency
- Alcoholic hepatitis

Product: Evolocumab
Protocol Number: 20130286
Date: 30 January 2017
Page 27 of 73

- Autoimmune hepatitis
- Wilson's disease and hemochromatosis
- Nonalcoholic fatty liver disease including steatohepatitis
- Nonhepatic causes (eg, rhabdomylosis, hemolysis)

Amgen IP (evolocumab/placebo) and other protocol-required therapies should be discontinued permanently and the subject should be followed according to the recommendations in Appendix A (Additional Safety Assessment Information) for possible DILI.

Rechallenge may be considered if an alternative cause for impaired liver tests (ALT, AST, ALP) and/or elevated TBL, is discovered and the laboratory abnormalities resolve to normal or baseline (Section 6.3.2).

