Table 1. Conditions for Withholding and/or Permanent Discontinuation of Amgen Investigational Product and Other Protocol-required Therapies Due to Potential Hepatotoxicity

Analyte	Temporary Withholding	Permanent Discontinuation
Total bilirubin	> 3x ULN at any time	> 2x ULN
		OR
INR		> 1.5 (for subjects not on anticoagulation therapy)
	OR	AND
AST/ALT	> 8x ULN at any time > 5x ULN but < 8x ULN for ≥ 2 weeks	In the presence of no important alternative causes for elevated AST/ALT and/or total bilirubin values
	> 5x ULN but < 8x ULN and unable to adhere to enhanced monitoring schedule	> 3x ULN (when baseline was < ULN)
	> 3x ULN with clinical signs or symptoms that are consistent with hepatitis (such as right upper quadrant pain/tenderness, fever, nausea, vomiting, jaundice)	
	OR	
ALP	> 8x ULN at any time	

ALP=alkaline phosphatase; ALT=alanine aminotransferase; AST=aspartate aminotransferase; INR=international normalized ratio; ULN=upper limit of normal.

Protocol Number: 20130286

Date: 30 January 2017

Page 28 of 73

6.3.2 Criteria for Rechallenge of Amgen Investigational Product and Other Protocol-required Therapies After Potential Hepatotoxicity

The decision to rechallenge the subject should be discussed and agreed upon unanimously by the subject, investigator, and Amgen.

If signs or symptoms recur with rechallenge, then evolocumab/placebo should be permanently discontinued. Subjects who clearly meet the criteria for permanent discontinuation (as described in Section 6.3.1) should never be rechallenged.

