Subjects with abnormal hepatic laboratory values (ie, alkaline phosphatase [ALP], AST, ALT, total bilirubin [TBL]) **and/or international normalized ratio (INR)** and/or signs/symptoms of hepatitis (as described below) may meet the criteria for withholding or permanent discontinuation of Amgen IP or other protocol-required therapies as specified in the Guidance for Industry Drug-Induced Liver Injury (DILI): Premarketing Clinical Evaluation (July 2009).

Section: 6.3.1 Criteria for Permanent Discontinuation of Amgen Investigational Product and Other Protocol-required Therapies Due to Potential Hepatotoxicity

Delete

- TBL ≥ 2x ULN
- AND increased AST or ALT ≥ 3x ULN from a baseline value were less than the ULN
- AND ALP < 2x ULN
- AND no other cause for the combination of the above laboratory abnormalities is immediately apparent; important alternative causes for elevated AST/ALT and/or TBL values include, but are not limited to:

Add:

6.3.1 Criteria for **Withholding or** Permanent Discontinuation of Amgen Investigational Product and Other Protocol-required Therapies Due to Potential Hepatotoxicity

The following stopping and/or withholding rules (Table 1) apply to subjects for whom another cause of their changes in liver biomarkers (TBL, INR and transaminases) has not been identified.

Important alternative causes for elevated AST/ALT and/or TBL values include, but are not limited to:

Product: Evolocumab
Protocol Number: 20130286
Date: 30 January 2017
Page 11 of 20

Table 1. Conditions for Withholding and/or Permanent Discontinuation of Amgen Investigational Product and Other Protocol-required Therapies Due to Potential Hepatotoxicity

Analyte	Temporary Withholding	Permanent Discontinuation
Total bilirubin	> 3x ULN at any time	> 2x ULN
		OR
INR		> 1.5 (for subjects not on anticoagulation therapy)
	OR	AND
AST/ALT	> 8x ULN at any time > 5x ULN but < 8x ULN for ≥ 2	In the presence of no important alternative causes for elevated AST/ALT and/or total bilirubin
	weeks	values
	> 5x ULN but < 8x ULN and unable to adhere to enhanced monitoring schedule	> 3x ULN (when baseline was < ULN)
	> 3x ULN with clinical signs or symptoms that are consistent with hepatitis (such as right upper quadrant pain/tenderness, fever, nausea, vomiting, jaundice)	
	OR	
ALP	> 8x ULN at any time	

ALP=alkaline phosphatase; ALT=alanine aminotransferase; AST=aspartate aminotransferase; INR=international normalized ratio; ULN=upper limit of normal.

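### Appendix A's 24-hour liver report rests on criteria that depend on cause and baseline, so laboratory-only cases in hepatitis C, atazanavir or indinavir subjects need not trigger it

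*Protocol*

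**What the plan says.** **Reporting rule.** Protocol Appendix A, under drug-induced liver injury (DILI) reporting, states that "cases of concurrent AST or ALT and TBL according to the criteria specified in Section 6.3 require the following". What follows is an SAE report to the sponsor within 24 hours, due "before additional etiologic investigations have been concluded". Other liver events are to be reported as SAEs only if they meet the seriousness criteria, which Appendix A places in Section 9.2.2.2.

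**Criteria it points to.** The numeric criteria are in Section 6.3.1 and Table 1. Section 6.3.1 says that these rules "apply to subjects for whom another cause of their changes in liver biomarkers (TBL, INR and transaminases) has not been identified". Table 1's permanent-discontinuation column is the only rule that combines transaminases with bilirubin (or INR). It adds the condition "In the presence of no important alternative causes for elevated AST/ALT and/or total bilirubin values" and sets the AST/ALT limb at "> 3x ULN (when baseline was < ULN").

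**Listed alternative causes.** Section 6.3.1 names "Viral hepatitis (eg, Hepatitis A/B/C/D/E, Epstein-Barr virus" and others, and also "drugs that inhibit bilirubin glucuronidation (eg, indinavir, atazanavir").

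**Who can enrol.** Under criterion 209 in Section 4.1.2, stable "chronic hepatitis C of at least 1 year duration prior to randomization is allowed", with AST and ALT below 5 times ULN. Section 5.1 stratifies randomisation by hepatitis C status. No criterion excludes atazanavir or indinavir by name, and Table 2 covers rosuvastatin dosing with ritonavir-boosted atazanavir.

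**SAP.** Section 10.6.2 counts subjects with ALT or AST ≥ 3x ULN together with total bilirubin ≥ 2x ULN and ALP < 2x ULN. It sets no condition on cause.

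**The concern.** Appendix A asks the site to report first and establish the cause afterwards. The criteria that open the rule ask about cause before they can be met. For most subjects the conflict may do no harm, because nothing is known about cause when the result arrives. In subjects with hepatitis C, or on atazanavir or indinavir, a listed alternative cause is already on record at screening. A site that reads Table 1 literally can conclude that the criteria are unmet, and that no mandatory report is due, for a new combined rise on treatment.

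What is at stake is uniform expedited reporting. Two sites could handle the same laboratory values differently, and the difference would fall partly along a randomisation stratum. Cases not classified as serious would also be absent from the SAP's serious adverse event tables.

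**Working it through.** No sample size, power or event count enters this point, so the check sets the passages side by side.

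**Step 1: which criteria apply.** Appendix A gives no thresholds of its own. Section 6.3 defers to Table 1, whose combined rule needs all of the following:

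| Condition in the permanent-discontinuation column | Source |
|---|---|
| Total bilirubin > 2x ULN, or INR > 1.5 if not anticoagulated | Table 1 |
| AST/ALT > 3x ULN | Table 1 |
| Baseline AST/ALT below ULN | Table 1 |
| No important alternative cause for AST/ALT and/or bilirubin | Table 1 |
| No other cause of the changes identified | Section 6.3.1 |

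Table 1's temporary-withholding limits fall under the same Section 6.3.1 scope sentence, so they do not avoid the condition on cause.

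**Step 2: apply them to subjects who can be enrolled.** Take AST/ALT > 3x ULN with bilirubin > 2x ULN on treatment.

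- *Hepatitis C, normal baseline transaminases.* The values are met. A listed cause is present, so the criterion can be read as unmet.
- *Hepatitis C, baseline AST/ALT from ULN to below 5x ULN (allowed by criterion 209).* The baseline condition fails as well, whatever view is taken of cause.
- *Atazanavir or indinavir user.* A listed cause exists for the bilirubin rise. Because Table 1 says and/or, a cause for bilirubin alone is enough for the criterion to be read as unmet.

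The baseline condition is a separate gap. It leaves out any subject whose baseline AST/ALT was at or above ULN, with or without hepatitis C.

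**Step 3: what remains if the trigger is not met.** Section 9.1.4 makes fatal, life-threatening, hospitalised and disabling events serious by definition, and Section 9.2.2.2 requires all SAEs to reach the sponsor within 24 hours. For events meeting none of those criteria, Section 9.1.4 lists DILI as an example that the investigator could classify as serious, and refers back to Appendix A for the reporting criteria. That is circular: the fallback returns the site to the trigger that was not met. Appendix A also cites Section 9.2.2.2 for the seriousness criteria, but that section gives reporting procedure; the definition is in Section 9.1.4.

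**Step 4: the INR limb.** Appendix A names bilirubin only, whereas Table 1 accepts bilirubin or INR. INR is not in the Table 4 analyte list, so scheduled laboratory tests would not supply it.

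**Step 5: what the SAP captures.** Section 10.6.2 tabulates combined elevations regardless of cause or baseline. It is a summary table, not an expedited report, and its definition differs from Table 1: ≥ instead of >, an added ALP condition, and no INR. Section 10.6.1 splits treatment-emergent adverse events by statin stratum; no hepatitis C split is stated for adverse events or for the laboratory categories.

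**The case against.** The strongest reply is that the text can be read sensibly as it stands. Section 6.3.1 speaks of the cause of the changes, not of a diagnosis held at screening. Criterion 209 requires hepatitis C to be stable with no new treatment expected, so a stable infection does not by itself explain a new rise. Appendix A places the search for alternative causes after the report, and Section 6.3.1 allows rechallenge when an alternative cause is discovered, which suggests that cause is settled later.

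Much of this stands. An investigator could reasonably report such a case, so the text supports only that the report need not be triggered. It does not settle the matter: Table 1 asks whether important alternative causes are present, which is less open to that reading, and the baseline condition does not depend on cause at all.

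Three stronger inferences are tempting and not supported:

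- *That mandatory reporting is disabled in these subjects.* The contestable wording and the outcome-based seriousness criteria rule this out.
- *That serious liver events reach the sponsor only at the investigator's discretion.* Discretion covers laboratory-defined cases that meet no outcome-based criterion.
- *That the stated 95% probability of detecting a 1% adverse event among 300 evolocumab subjects is reduced.* Adverse event collection under Sections 9.1.2 and 9.2.2.1 carries no condition on alternative cause, so no subject leaves that denominator.

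Nor do the documents say that these subjects have less hepatic reserve, or that this combination is the trial's principal liver signal. Enrolment of indinavir users is inferred only from the absence of an exclusion.

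**Conclusion.** The point holds as an internal conflict in the reporting rule. Appendix A wants a report before cause is established, yet takes its trigger from criteria that depend on cause and on baseline transaminases. For subjects with hepatitis C, on atazanavir or indinavir, or with baseline AST/ALT at or above ULN, a laboratory-defined combined elevation without an outcome-based seriousness criterion need not trigger the mandatory report.

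The number affected cannot be derived, because the documents give no share for any of these groups; the conclusion does not need one. What could be lost is consistent 24-hour SAE reporting of such cases, not their detection: chemistry is still measured centrally at scheduled visits, and the combined elevations are still tabulated. The conclusion assumes that a site may read Table 1 literally, which its wording permits but does not compel. The correction is worth making because it is cheap and concerns safety reporting.

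**What to change.** 1. Reconcile Appendix A with Section 6.3.1 and Table 1 so that the reporting trigger is stated separately from the stopping rules. It should rest on the laboratory values and apply irrespective of presumed or pre-existing cause, with any alternative cause recorded in the narrative.
2. Have the sponsor's safety physician state how the trigger applies when baseline AST/ALT is at or above ULN. Removing the condition on cause alone would still leave these subjects out. Simply dropping the baseline condition also needs thought, since a hepatitis C subject admitted between 3x and 5x ULN already exceeds the transaminase limb at entry.
3. Have the safety physician state whether the INR limb applies to reporting, given that INR is not in Table 4.
4. Correct the seriousness cross-reference in Appendix A from Section 9.2.2.2 to Section 9.1.4.
5. Tabulate the SAP Section 10.6.2 combined category by hepatitis C stratum.

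Whether a cause already present at randomisation also affects the Table 1 stopping rules is a separate question for the sponsor to reconcile; no stopping rule is proposed here.

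The cost is a short rewording of Appendix A, one corrected reference and one table split. The downside is a few more SAE reports, some of which will prove unrelated to treatment.
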